8.7 Concomitant Therapy

All concomitant medications and any therapies (prescribed and non-prescribed) must be recorded on the CRF. Any change during the study should be documented as well. Symptomatic treatment of side effects and treatment of concomitant diseases not associated with leishmaniasis is permitted. Treatment with other agents known or likely to be active against *Leishmania* (pentavalent antimony, amphotericin B, paromomycin, imidazoles, local heat or cold therapy) is not permitted.

8.8 Rescue Treatment

Anti-leishmaniasis drugs must not be administered while the subject is on protocol. If the subject is removed from the protocol for any reason (decision that the subject has failed treatment, inability of the subject to comply with the protocol conditions, or desire of the subject, physician, Sponsor, or IRB), the subject may be treated with another antileishmanial agent off-protocol at the discretion of the treating physician.

9 STUDY PROCEDURES

Time and Event Schedule									
Study Phase	Screening ^a		Treatment			Follow-up			
Study Day/Week/Month	Day -14 to -1	Day 1	Day 7 ± 3 days	Day 14± 3 days	Day 28	Week 6	Month 3	Month 7	Month 13 ^h
Informed Consent	Х								
Demographics	Х								
Medical History ^{b, c}	Х	Х	Х	X	Х	Х	Х	Х	Х
Physical examination ^d	Х	Х			Х	Х	Х	Х	Х
Leishmanial History and Exam ^c	Х				Х	X	Х	Х	Х
Hematology	Х								
Blood Chemistries	Xe			X ^f	\mathbf{X}^{f}	X ^g	X^{g}	X ^g	X ^g
ECG	Х								
Pregnancy Test	Х	Х	Х	X	Х		Х	Х	
Eligibility Checklist	Х								
AEs		Х	Х	Х	Х	Х	X	X	Х
Treatment			Daily						

^aScreening includes the 14-day period for conducting screening procedures prior to the first administration of investigation product on Day 1.

^bIncludes medication history

^cIf subject does not appear at the scheduled Week 6, Month 3, Month 7, or Month 13 visits, these data may be obtained from the subject by telephone, and will be noted as obtained in that manner.

^dIncludes vital signs

^eScreening laboratories

^fAlanine transaminase (ALT) and creatinine on Day 28 and also on nominal day 14

^gIf abnormal on previous examination

^hML subjects only

9.1 Subject Recruitment

The medical community will be alerted to the availability of miltefosine via this Treatment IND via informal communications and listing on ClinicalTrials.gov.

Subjects with mucosal or cutaneous lesions from which Leishmania have already been identified are potentially eligible to be treated with miltefosine via this protocol. Treating Physicians with potentially eligible subjects will contact the protocol PI, and receive the CRFs from the PI. The Treating Physician will complete the screening CRF pages for demographics, medical history, leishmaniasis history, clinical laboratory results that are available, and identification of Leishmania in the lesion, and send (mail or fax) these CRF pages to the PI. If after PI review, the subject is potentially eligible for the protocol, the PI will send the protocol, the miltefosine package insert, the informed consent form, and the FDA form 1572 to the Treating Physician. Although this protocol will have already been approved by a "central" IRB, if there is an additional need to have the Treating Physician's local IRB approve the protocol, the Treating Physician will obtain the approval, and obtain informed consent from the subject. The rest of the laboratory tests must be accomplished so that all screening laboratory tests are completed prior to enrolling a potential subject. If in the physician's opinion the subject appears eligible for enrollment, the Treating Physician will send the local IRB signature page (if needed), protocol signature page, informed consent signed by both the subject and the Treating Physician, the rest completed CRF pages for screening data to the PI, and the form 1572 completed with the Treating Physician's information plus his/her curriculum vitae. After the PI's review of these documents, the investigational product will be sent from the drug repository to the Treating Physician for that subject's use.

Note that because the tests needed to satisfy the entrance criteria of medical history, leishmaniasis history, and identification of *Leishmania* in the lesion are standard of care for this disease, the tests can be performed prior to signing the consent form for this protocol. This procedural order [evaluate certain entrance criteria, then achieve local IRB approval if needed and signing of consent, then evaluate the rest of the entrance criteria] is chosen so that subjects do not undergo excess procedures and expectations if the subject ultimately is unlikely to be able to enroll in the protocol.

9.2 Screening Procedures

Subjects will have the following procedures performed during a two week period prior to the initiation of investigational product:

- 1. Consent form completed and signed.
- 2. Demographics form completed.
- 3. Medical history form completed and record medications used in the past 2 weeks.
- 4. Physical examination form completed including vital signs, height, and weight.
- 5. Leishmaniasis history and physical form completed.
 - a. Record history of leishmaniasis including;
 - (1) CL: estimated date that the lesion(s) first appeared, evolution of symptoms, treatments to date
 - (2) ML: estimated date that the symptoms first appeared, evolution of symptoms, treatments to date

- b. CL subject examination: For each cutaneous lesion, record the size of the lesion ulceration (length/width), characteristics of the lesion (ulcerated versus non-ulcerated), and anatomical location. Examination of nasal skin, nasal mucosa, palate, and pharynx must be performed by the Treating Physician.
- c. ML subject examination: Examination of mucosal membranes. Each of 5 possible sites (nasal skin, nasal mucosa, palate, pharynx, and larynx) will be evaluated for 4 possible signs of disease (erythema, edema, infiltration, and erosion) by an ear, nose, and throat (ENT) specialist.
- 6. Pregnancy test from completed for women of child-bearing potential.
- 7. Hematology form completed to include white blood cells (WBC), neutrophil count, hemoglobin, hematocrit, and platelet count.
- 8. Chemistry form completed including glucose, sodium, potassium, creatinine, ALT, and bilirubin in the serum.

9.3 Assessment During Miltefosine Treatment

9.3.1 Study Day 1

Study Day 1 visit is conducted on the first day of miltefosine therapy and includes:

- 1. Medical History record changes in medical history or medications since screening visit
- 2. Physical Examination form perform brief physical exam including vital signs
- 3. Pregnancy test form perform a pregnancy test in women of child bearing potential, unless the screening pregnancy test was performed within the previous 24 hours.
- 4. Complete the eligibility checklist to ascertain if the subject still meets all of the eligibility criteria, then the subject will receive the first dose of medicine.
- 5. Record any AEs

9.3.2 Study Days 7 and 14

Two visits are scheduled to occur between Study Day 2 through Study Day 27 and should preferably occur at the end of Study Week 1 and Study Week 2 with in a three-day window either side of Day 7 and Day 14. At these two visits the following assessments are performed:

- 1. Medical History The subject will return to clinic for evaluation; record any AEs
- 2. Treatment form complete log
- 3. If more medication than that which was dispensed on day 1 is needed, further medication will be dispensed on the nominal day 14 visit
- 4. Chemistry record values of ALT and creatinine in the serum (Day 14 visit only)
- 5. Record any AEs

9.3.3 Study Day 28

Study Day 28 visit is conducted the last day of miltefosine therapy and includes:

- 1. Medical History record changes in medical history or medications
- 2. Physical examination record vital signs
- 3. Interval History of leishmaniasis:
 - a. CL lesion reactions
 - b. ML evolution of symptoms
- 4. CL subjects: Re-examination of each CL lesion and re-recording the size of the lesion ulceration (length/width), other notable characteristics of the lesion

- 5. ML subjects: Re-examination of mucosal membranes
- 6. Pregnancy test in women of child-bearing potential
- 7. Chemistry record values of ALT and creatinine in the serum
- 8. Record any AEs

9.3.4 Study Week 6

Two weeks after the Study Day 28 visit record the following:

- 1. Medical History record changes in medical history or medications since 28-day visit
- 2. Physical examination perform brief physical exam if appropriate, and vital signs
- 3. Interval History of leishmaniasis since last visit to include:
 - a. ML re-examination of mucosal membranes. Evolution of symptoms
 - b. CL subjects re-examination of each CL lesion and record the size of the lesion ulceration (length/width), other notable characteristics of the lesion
- 4. ALT and creatinine: Repeat if abnormal on last examination
- 5. Record any AEs

9.3.5 Study Month 3

Study Month 3 visit is conducted 2 months after the end of miltefosine therapy and includes:

- 1. Medical History record changes in medical history or medications since 6-week visit
- 2. Physical Examination perform brief physical exam if appropriate, and vital signs
- 3. Interval History of leishmaniasis since last visit to include:
 - a. ML re-examination of mucosal membranes. Evolution of symptoms.
 - b. CL subjects re-examination of each CL lesion and record the size of the lesion ulceration (length/width), other notable characteristics of the lesion
- 4. Pregnancy test in women of child bearing potential
- 5. ALT and creatinine: Repeat if abnormal on last examination
- 6. Record any AEs

9.3.6 Study Month 7

Study Month 7 visit is conducted 6 months after the end of miltefosine therapy. Final follow up visit for CL subjects and includes:

- 1. Medical History record changes in medical history or medications since 3-month visit
- 2. Physical Examination perform brief physical exam if appropriate, and vital signs
- 3. Interval History of leishmaniasis since last visit to include:
 - a. ML re-examination of mucosal membranes. Evolution of symptoms
 - b. CL subjects re-examination of each CL lesion and record the size of the lesion ulceration (length/width), other notable characteristics of the lesion
- 4. Pregnancy test in women of child bearing potential
- 5. ALT and creatinine: Repeat if abnormal on last examination
- 6. Record any AEs

9.3.7 Study Month 13

Study Month 13 visit is conducted 12 months after the end of miltefosine therapy. Final follow up visit for ML subjects and includes:

- 1. Medical History record changes in medical history or medications since 7-month visit
- 2. Physical Examination perform brief physical exam if appropriate, and vital signs

- 3. Interval History of leishmaniasis since last visit to include:
 - a. ML re-examination of mucosal membranes. Evolution of symptoms.
 - b. CL subjects re-examination of each CL lesion and record the size of the lesion ulceration (length/width), other notable characteristics of the lesion
- 4. ALT and creatinine: Repeat if abnormal on last examination
- 5. Record any AEs

NOTE: if the subject does not return to clinic for the post-treatment visits, medical history and interval history of leishmaniasis may be obtained by telephone. Further, the subject's examination of a CL lesion may be obtained by telephone. Telephonic data will be noted as such on the CRF.

10 EFFICACY

NOTE: Responses in subjects with CL and ML will be presented separately.

10.1 Efficacy Assessments of CL Subjects

10.1.1 Assessment Methods

10.1.1.1 Parasitological Diagnosis of Leishmaniasis

Prior to entrance into this protocol, lesion(s) will have been scraped, aspirated, or biopsied; and the specimens will have been smeared onto microscope slides for examination with DifQuik or Giemsa staining, placed in culture medium to visualize motile promastigotes, or subjected to PCR analysis for *Leishmania*-specific nucleic acid.

NOTE: The Treating Physician may choose to perform these parasite diagnostic procedures on lesions that are not-healed post therapy or on a new lesion to see if the lesion contains *Leishmania*. These procedures are at the Treating Physician's discretion and not formally part of this protocol.

10.1.1.2 Examination of Cutaneous Lesions

Ulcerated CL lesions will be measured in mm for the longest diameter and perpendicular width of ulceration. Non-ulcerated lesions will be measured for length and width of the raised area of the lesion. Lesion area = Length x Width. Lymph nodes in the drainage path of the cutaneous lesion will be noted and measured.

10.1.1.3 Examination of Mucosa

For CL subjects, the Treating Physician will examine the nasal and oral mucosa of each subject.

10.1.2 Definitions of Lesion Response

Healed:	100% reduction in lesion area [lesion size = $0x0 \text{ mm}^2$]
Improved:	50% - 99% reduction in lesion area
No change:	49% enlargement to 49% reduction in lesion area
Worse:	>50% enlargement of lesion area at or after the end of therapy.
Relapsed:	Substantial enlargement of lesion after initial improvement or healing.

10.1.3 Definition of Clinical Responses

Lesion Cure: Lesion is healed at the Month 7 visit.

Lesion Failure: Each lesion will be considered a failure if it does not meet the criteria for cure (missing data will be considered failures). The intended response to therapy is a progressive diminution in lesion size and no relapse. Lesion failure therefore is defined as clinically worse at the end of therapy or thereafter, OR does not improve at the Week 6 or Month 3 visit, OR is not healed at the Month 7 visit, OR relapses.

NOTE: Parasitological responses can assist the clinician in evaluating the clinical response of the lesion. If the Treating Physician has parasitologically re-investigated a slowly responding lesion

at time-points greater than 2 weeks after the end of therapy, and parasites are still present by microscopy or culture, the physician may interpret the data as indicating therapeutic failure. Note that the presence of parasites prior to 2 weeks after the end of therapy should not be interpreted. Note that because PCR is more sensitive than microscopy or culture on which the clinical experience in the literature is based, PCR positivity post therapy cannot easily be interpreted.

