10.1.4 Definition of Subject Cure

Subject Cure: All lesions cured by the end of follow up at Month 7 visit. *Subject Failure:* Not all lesions clinically cured, or a new lesion due to *Leishmania*.

Primary endpoint(s): The co-primary endpoints are the subject cure rate for the modified intention-to-treat (mITT) and evaluable populations.

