10.2.3 Definition of Subject Responses

Subject cure: Clinical cure is lesion is healed.

Subject failure: Leasion did not heal. NOTE: The intended response to therapy is a progressive diminution in signs and symptoms and no relapse. Subject failure is defined as clinically worse at the Week 6 visit or thereafter, OR does not improve at the Month 3 or month 7 visits, OR is not healed at the Month 13 visit, OR relapses.

Primary endpoint(s): The primary endpoints are the clinical cure rates for the mITT and evaluable population.

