12.2 Analytical Populations

mITT Population: The mITT population includes all subjects who received any administration of an investigational product.

Evaluable Population: The evaluable population will include all subjects who received daily doses of investigational product for at least 25 of the total of 28 days, had lesion measurements at the Month 7 for CL or the month 13 visit for ML, and who did not receive rescue medications to treat leishmaniasis at any time during the study.

Efficacy outcomes will be presented separately for subjects with CL and ML.

Safety Population: The safety population includes all subjects who received any administration of investigational product.

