12.6.3 Handling of Missing Data

Missing lesion measurements will be ignored when presented as summary statistics of lesion areas and lesion responses as presented by numbers of lesions evaluated at each time point. Subjects who do not provide lesion response measurements at their final scheduled follow up will be considered lesion ane subject failures in the mITT analysis.

Note that if a subject does not appear at the scheduled Study Week 6, Month 3, or Month 7 visits, the subject's estimate of his/her lesion response may be obtained from the subject by telephone, and will be noted as obtained in that manner. Such data is not defined as missing. For such data, the Treating Physician and the PI will jointly decide if the subject's estimate is likely to be reliable. In a single-group non-comparative study such as this one, errors in interpretation will only apply to miltefosine subjects and will not be corrected by being equally applied to a comparator group. Therefore, it is important for subject, physician, and Investigator to avoid two potential errors: 1) erroneously viewing a lesion as healed when in fact it is still present, 2) erroneously viewing a lesion as failed because a subject does not show up for clinic, when in fact the lesion has healed and the subject does not want to spend time coming to clinic.

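### The mITT cure rate has no rule for rescue, so a subject rescued without meeting a listed failure criterion and read as healed at the end can count as a miltefosine cure

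*Combined protocol and SAP*

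**What the plan says.** - **Endpoints.** Section 10.1.4 (CL): "The co-primary endpoints are the subject cure rate for the modified intention-to-treat (mITT) and evaluable populations". Section 10.2.3 (ML): "The primary endpoints are the clinical cure rates for the mITT and evaluable population".
- **Cure.** Section 10.1.3: "Lesion Cure: Lesion is healed at the Month 7 visit"; 10.1.4 requires this of every lesion. For ML, 10.2.3: "Subject cure: Clinical cure is lesion is healed".
- **Failure.** For CL, 10.1.3 fails a lesion that is worse at or after the end of treatment, has not improved at Week 6 or Month 3, is not healed at Month 7, or relapses. Section 10.1.4 adds a new leishmanial lesion. For ML, 10.2.3 fails a subject who is worse from Week 6 on, has not improved at Month 3 or 7, is not healed at Month 13, or relapses. Neither list mentions rescue or early stopping.
- **Populations.** Section 12.2: "The mITT population includes all subjects who received any administration of an investigational product". The evaluable population needs at least 25 of 28 days of dosing, a Month 7 or Month 13 measurement, and that the subject "did not receive rescue medications to treat leishmaniasis at any time during the study".
- **Rescue.** Section 8.8 bars other antileishmanial drugs on protocol. After removal for any reason, "the subject may be treated with another antileishmanial agent off-protocol at the discretion of the treating physician". The reasons it names include inability to comply and the wish of the subject or physician, as well as treatment failure. Under 8.6, a subject who cannot tolerate the dose goes off treatment.
- **Missing data.** Section 12.6.3 (CL): "Subjects who do not provide lesion response measurements at their final scheduled follow up will be considered lesion" and subject failures in mITT; 12.7.3 has the same rule for ML. A CL telephone report does not count as missing, and its reliability is judged jointly by the Treating Physician and the PI. ML telephone examinations are not accepted.

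**The concern.** The trial has one arm, and the mITT rate is meant to record what miltefosine achieves in everyone who started it. If a subject switches to another agent and the later healing is credited to miltefosine, the rate no longer measures that. No control arm carries the same error, a weakness of single-group data that 12.6.3 itself acknowledges.

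The plan handles rescue in one population only. The evaluable analysis removes rescued subjects from numerator and denominator, and the mITT rules are silent. No planned analysis therefore explicitly scores rescue as a failure. Two analysts could also score the same subject differently, and the result can depend on whether the site obtained a final reading after the subject left.

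**Working it through.** The plan states no target cure rate, power or sample-size calculation (12.1), so there is no design figure to reproduce. The check is to follow one subject through the rules and then size the effect.

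**Step 1: the subject.** A CL subject stops miltefosine early, is removed at their own wish, receives another agent off-protocol, has improved at Week 6 and Month 3, and is healed at Month 7.

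| Rule | Effect on this subject |
|---|---|
| mITT membership (12.2) | Included: at least one dose taken |
| Worse, not improved, relapsed, new lesion (10.1.3, 10.1.4) | None met |
| Healed at Month 7 (10.1.3) | Met: lesion cure, and subject cure if all lesions are healed |
| Missing final reading (12.6.3) | Does not apply |
| Rescue (12.2) | Acts on the evaluable population only |

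Result: an mITT cure. An ML subject who has improved at Months 3 and 7 and is healed at Month 13 follows the same path. Without a final reading, either subject is a failure.

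**Step 2: how a subject can reach rescue without a failure criterion.**
- Intolerance, with treatment stopped (8.6) and removal from protocol.
- Inability to comply, or the wish of the subject or physician (8.8).
- A slowly responding CL lesion in which parasites are still found more than 2 weeks after treatment. The note in 10.1.3 lets the physician read this as therapeutic failure, but it is not in the failure list. A lesion 50% to 99% smaller is classed as improved (10.1.2), so it can pass Week 6 and Month 3.

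**Step 3: who is already a failure.** Section 10.3 says that withdrawal for lack of efficacy will generally rest on the listed failure criteria, so most subjects rescued for inefficacy have met one. This protection has a gap. A lesion that met an interim failure criterion and is healed at Month 7 satisfies both the cure sentence and the failure list in 10.1.3, and no precedence is stated. The ML definitions in 10.2.3 overlap in the same way.

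**Step 4: size.** Planned total (7.1.1): 10 x 1 = 10 to 20 x 5 = 100 subjects, CL and ML together. With r affected subjects, shift = r/N.

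| N | Shift for r = 1 |
|---|---|
| 10 | 1/10 = 10 points |
| 20 | 1/20 = 5 points |
| 50 | 1/50 = 2 points |
| 100 | 1/100 = 1 point |

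CL and ML are presented separately (12.2), so the real denominators are smaller and the shift per subject is larger.

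Illustration, assuming a literal mITT cure rate of 80% (exact 95% intervals, which the plan itself does not call for):
- N=20, r=0: 16/20 = 80% (56.3 to 94.3)
- N=20, r=1 scored as failure: 15/20 = 75% (50.9 to 91.3)
- N=20, r=2 scored as failures: 14/20 = 70% (45.7 to 88.1)
- N=100, r=2 scored as failures: 80/100 = 80% (70.8 to 87.3) becomes 78/100 = 78% (68.6 to 85.7)

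In the N=20, r=2 case, if the other 18 subjects are all evaluable, the evaluable rate is 14/18 = 77.8%. It leaves out the rescued cures but does not count the two subjects as failures.

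**The case against.** The strongest reply is that the plan's default path already leads to failure. Rescue comes only after removal (8.8). Section 8.6 then asks for one assessment, or one visit for lesion measurements, and nothing schedules a removed subject for Month 7 or Month 13. Without that reading the subject is an mITT failure. Telephone reports need a joint reliability decision for CL and are barred for ML. The study is descriptive (12.3), the evaluable rate excludes rescued subjects, and a separate statistical analysis plan is still to be written (section 14).

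Most of this stands, and it narrows the problem. It does not close it: when a final reading is obtained, the written rules give a cure, and the evaluable analysis only drops such subjects.

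Three stronger readings are tempting and are not supported:
- **Every rescued subject who heals is counted as a cure.** Many will have met an interim failure criterion or will have no final reading. Nor does the separate rescue condition in the evaluable definition prove that final readings after rescue were expected; conditions in a population definition can overlap.
- **The inflation is about 4 to 14 points.** A reader might assume that 5% to 15% of subjects fall in this group and apply the antimony cure rates quoted in the background: 0.05 x 0.75 = 3.8 points and 0.15 x 0.94 = 14.1 points. The documents give no such frequency. The 94% is 15/16 evaluable subjects; on all 18 it is 15/18 = 83%, and the upper figure would be 0.15 x 0.83 = 12.5 points.
- **The healing is due to the other drug.** The background reports self-healing (4.1.3), 38% cure on placebo in Colombia, and 14/14 cured after 20 days of miltefosine. The cause of healing after rescue cannot be known; the fault is that the plan credits it to miltefosine by default.

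**Conclusion.** The point holds in a limited form. Read literally, the mITT primary cure rate for CL and for ML can include a subject who left miltefosine for a reason outside the failure lists, was given another antileishmanial agent, met no interim criterion, and was read as healed at the end. The error can only raise the rate relative to scoring rescue as failure.

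The size rests on an unknown count, so only the effect per subject can be stated: 1 to 10 points over the planned total of 100 down to 10 subjects, and more within CL or ML alone. No overall inflation figure should be quoted. The view that most efficacy-driven rescues are already failures assumes that the failure list outranks later healing, which the plan should say. The evaluable rate contains no rescued cures.

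**What to change.** In 10.1.4, 10.2.3, 12.6.3 and 12.7.3, and in the analysis plan still to be prepared:

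1. State that a subject who receives any other antileishmanial treatment between Day 1 and the final visit is scored as a failure in the mITT analysis, whatever the later lesion status.
2. State that meeting any listed failure criterion takes precedence over healed status at the final visit.
3. Report the number of rescued subjects and list their final status, so that a reader can see the effect of the rule.
4. Record other antileishmanial treatment at any contact after removal.

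When rescue may be given does not change. The cost is a few sentences and little new data: concomitant therapies are already on the CRF (8.7), and medication changes are recorded at the Month 7 and Month 13 visits (9.3.6, 9.3.7), so a subject seen at the final visit should have the information. Item 4 is a small addition, because nothing clearly collects off-protocol treatment after removal. The downside is that the mITT rate may be slightly lower, and some rescued subjects who would have healed on miltefosine or spontaneously will count as failures. The listing in item 3 makes that visible.
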